- m. During the Baseline Visit, participants randomly assigned to ceftriaxone plus azithromycin will receive a single IM dose of ceftriaxone (500 mg) plus a single oral dose of azithromycin (1 g). See Section 7.1. Azithromycin should be taken after food consumption and with water.
- n. Record serious adverse events from the time of consent/assent in order to fulfill international regulatory requirements.
- o. Record adverse events from the time of the first dose of study treatment.
- p. Confirm return day/time for the TOC and Follow-up Visits.
- q. Previsit reminder: Study site staff will contact the participant 24 ± 4 hours before the respectively scheduled Baseline (if applicable), TOC, or Follow-up Visit.
- r. Participants who tested positive for CT and/or Mgen per NAAT results at the Baseline Visit should be treated per local standard of care at or after the TOC Visit or at the Follow-up Visit (if treatment has not already been initiated), as required, after all study procedures at the visit have been completed.
- s. Collect sample only if the participant has a signed consent/assent specific for this purpose. The Baseline Visit is the recommended time to collect the sample; however, it can be collected at any time during the study.

Table 2 Collection of Bacteriology and NAAT Microbiological Specimens

Visit	Baseline	TOC ^a	Follow-up	Early Withdrawal
Study Day	1	4 to 8	14 to 21	NA
Collection Type Anatomical Site ^b – Organism	Pre-dose	NA	NA	NA
Bacteriology sample collection ^b				
Urogenital – NG ^c	X	X		X
Pharyngeal – NG ^d	X	X	X ^e	X
Rectal – NG ^d	X	X		X
NAAT assay sample collection ^f				
Urogenital – NG and CT ^g	X	X ^h		X
Urogenital – Mgen ^g	X		X ⁱ	X
Pharyngeal – NG and CT ^j	X	X	X ^k	X
Rectal – NG and CT ^j	X	X		X

CT=*Chlamydia trachomatis*; Mgen=*Mycoplasma genitalium*; NA=not applicable; NAAT=nucleic acid amplification test; NG=*Neisseria gonorrhoeae*; TOC=Test-of-Cure.

- Any participant that withdraws before TOC should have all bacteriology and NAAT assay collections performed as indicated at the TOC Visit.
- Multiple swab specimens and types may need to be obtained from each anatomical site; refer to the laboratory manual.

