8. DISCONTINUATION CRITERIA

8.1. Discontinuation of Study Treatment

Participants may voluntarily discontinue study treatment at any time. The investigator may also, at his or her discretion, discontinue the participant from study treatment at any time and initiate appropriate alternative therapy.

Reasons for study treatment discontinuation may include the following:

- Adverse event
- Protocol deviation
- Termination of the study by GSK
- Investigator discretion

The reason for study treatment discontinuation will be recorded in the eCRF. Participants who discontinue study treatment for the reasons above will not be considered withdrawn from the study and should return to the study site to complete the TOC and Follow-up Visits (see Table 1).

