- **TOC (Day 4 to 8) Visit:** Participants will be instructed to return to the study site 3 to 7 days following study treatment administration at Baseline in order to complete the TOC Visit. Assessments will be performed as shown in Table 1, including the following:
 - The TOC Visit will be preceded by a documented reminder contact from the study site to the participant 24±4 hours before the scheduled appointment time per the method (e.g., text message, telephone call, e-mail) confirmed with the study site staff prior to departing the study site on Day 1.
 - Specimens for microbiological testing will be collected as described in Section 9.1 and Table 2.
 - Participants may return to the study site before the scheduled TOC Visit due to AEs.
 - Participants testing positive for a CT and/or Mgen infection per baseline NAAT results should be treated, as required, per local standard of care at the TOC Visit only after completion of all visit procedures or at any point after the TOC Visit.
 - Participants with culture-confirmed bacterial persistence of urogenital and, as appropriate, pharyngeal and/or rectal NG should receive appropriate alternative therapy per the investigator's choice either on or after the TOC Visit, based on availability of results.
- **Follow-up (Day 14 to 21) Visit:** Participants will be instructed to return to the study site 14 to 21 days following study treatment administration at Baseline in order to complete the Follow-up Visit. Assessments will be performed as shown in Table 1, including the following:
 - The Follow-up Visit will be preceded by a documented reminder contact from the study site to the participant 24±4 hours before the scheduled appointment time per the method (e.g., text message, telephone call, e-mail) confirmed with the study site staff prior to departing the study site on Day 1.
 - The investigator and/or study site staff should make every effort to ensure a participant returns for this visit. If it is determined that the participant is unable to return to the study site, the Follow-up Visit assessments may be completed via telephone, with the exception of assessments requiring sample collection for laboratory testing.
 - Specimens for microbiological testing will be collected as described in Section 9.1 and Table 2.
 - Participants may return to the study site before the scheduled Follow-up Visit due to AEs or if they feel they are not responding to any alternative therapy started after the TOC Visit.

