Micro-ITT Rectal Population	
 • Participants who meet the definition of the Micro-ITT Population and have confirmed NG isolated that is ceftriaxone susceptible from baseline culture of their rectal specimen. • Participants will be analyzed according to their randomized study treatment. 	
 • Efficacy
Micro-ITT Pharyngeal Population	
 • Participants who meet the definition of the Micro-ITT Population and have confirmed NG isolated that is ceftriaxone susceptible from baseline culture of their pharyngeal specimen. • Participants will be analyzed according to their randomized study treatment. 	
 • Efficacy
Microbiologically Evaluable (ME) Population	
 • Participants who meet the definition of the Micro-ITT Population and follow important components of the study (i.e., (1) receive all planned doses as randomized and actual treatment is the same as randomized, (2) have a urogenital specimen collected at the TOC Visit, with available culture results, (3) have not taken any other systemic antibiotic prior to TOC, unless it was taken for the current infection, and (4) have no major deviation that prevents evaluation of efficacy). • Participants will be analyzed according to their randomized treatment arm. 	
 • Efficacy
Microbiologically Evaluable (ME) Rectal Population	
 • Participants who meet the definition of the Micro-ITT Rectal Population and follow important components of the study (i.e., (1) receive all planned doses as randomized and actual treatment is the same as randomized, (2) have a Rectal specimen collected at the TOC Visit, with available culture results, (3) have not taken any other systemic antibiotic prior to TOC, unless it was taken for the current infection, and (4) have no major deviation that prevents evaluation of efficacy). • Participants will be analyzed according to their randomized treatment arm. 	
 • Efficacy

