5.6. Analysis Visits

Due to participants potentially returning outside the protocol scheduled visit window, analysis visit windows will be defined for by-visit summaries and analysis purposes as illustrated in the table below. Data not reported by-visit, including adverse events and concomitant medications, will not employ analysis visits. Analysis visit labels will be assigned to each post-baseline record (including records from unscheduled and early termination visits) based on the corresponding study day (relative to first study treatment or randomization if not treated). For post-baseline records collected outside the analysis visit window, a blank analysis visit label will be assigned. For example, a record collected at study Day 11 will not be utilized in any analyses conducted at the TOC or FU scheduled visit. Descriptive summaries that are shown for “any assessment post baseline” e.g., maximum/minimum/ worst case post baseline, will use all assessments irrespective of whether they fall in an analysis visit window. There are no scheduled FU assessments for Urogenital (except Mgen participants) or rectal body site, but it is possible that any unscheduled assessment or a late TOC fall into this FU window and in that case FU visit will not be presented in summaries but in listings it will be included.

Scheduled Post-baseline Visit	Protocol Window	Target Day	Analysis Visit Window (Days)
Test-of-Cure	4 to 8	6	4 to 10
Follow-up	14 to 21	18	13 to 24

If multiple records exist within the same analysis visit window, then the record occurring closest to the target day will be utilized in all analyses and analysis population determinations. If multiple records are equally close to the target day, then the later record will be utilized. If multiple records occur on the same day and time is not collected, then the record with the larger Study Data Tabulation Model (SDTM) record sequence number will be utilized in all analyses. All protocol scheduled assessments (including unscheduled and early termination visits) will be presented in subject listings. Both the nominal and analysis visit will be presented in listings.

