7.1.1. Endpoint / Variables

The primary efficacy endpoint is culture-confirmed bacterial eradication of NG from the urogenital body site (i.e., microbiological success) at the TOC visit.

- Only those participants who have central laboratory confirmed NG from culture of their baseline bacteriology specimen will be evaluated for microbiological outcome and response. Ceftriaxone susceptibility will be evaluated by applying CLSI MIC breakpoints to results from ceftriaxone agar dilution testing. If an agar dilution value is not available for ceftriaxone, CLSI disk diffusion breakpoints will be applied to results from ceftriaxone disk diffusion testing. The microbiological outcome and response to study treatment will be determined by prespecified programmed algorithm for each participant (see Table 2).
- The microbiological outcome is determined by comparing the baseline culture results to the respective culture results at the TOC visit. The corresponding microbiological response (success or failure) “by participant” is then assigned. The criteria of microbiological participant level outcome and response is shown in Table 2.
- Participant level microbiological success refers to participants who have been deemed a “microbiological success” based on their microbiological response. All other participants are deemed “microbiological failures” for participant level microbiological response.

Table 2 Microbiological Outcome and Response at the Test-of-Cure Visit

Defining Criteria	Microbiological Outcome	Microbiological Response
Culture-confirmed elimination of baseline pathogen (NG) from a bacteriology sample taken at the TOC visit without the participant receiving other systemic antimicrobials before this visit	Bacterial eradication	Microbiological success
Culture-confirmed persistence of baseline NG pathogen from a bacteriology sample taken at the TOC visit without the participant receiving other systemic antimicrobials before this visit	Bacterial persistence	Microbiological failure
1) A determination of the TOC NG pathogen microbiological outcome cannot be made (e.g., no bacteriological sample taken for culture, sample lost, visit did not occur etc.) 2) The participant received other systemic antimicrobials before the TOC visit	Unable to determine	Microbiological failure

1. TOC=Test-of-Cure.
2. Note: A bacteriological specimen refers to a urogenital specimen obtained for bacteriological culture.

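### ME criterion 2 drops participants whom criterion 3 deliberately keeps: those treated early for the same infection, failures by rule, leave the supplementary ME analyses if they have no TOC culture

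*SAP*

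**What the plan says.** SAP Section 4 defines the ME population as Micro-ITT participants who meet four joint criteria; protocol 10.3 has the same list. Criterion 1 requires all planned doses of the randomized treatment. Criterion 2 is that participants "have a urogenital specimen collected at the TOC Visit, with available culture results". Criterion 3 is that they "have not taken any other systemic antibiotic prior to TOC, unless it was taken for the current infection". Criterion 4 excludes major deviations that prevent evaluation of efficacy. The ME Rectal and ME Pharyngeal sets repeat the wording for their own sites.

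The closing text of SAP Section 4 confirms that the antibiotic exclusion is aimed at agents not given for the current infection. The only note there on criterion 2 tightens it: an out-of-stability NG-negative TOC sample is not an available result.

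SAP Table 2 (Section 7.1.1; protocol Table 5) assigns the outcome Unable to determine and the response Microbiological failure when "The participant received other systemic antimicrobials before the TOC visit".

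SAP 5.6 sets the TOC analysis window at Day 4 to 10. Outside it, "For post-baseline records collected outside the analysis visit window, a blank analysis visit label will be assigned". Within a window, "the record occurring closest to the target day will be utilized in all analyses and analysis population determinations", so the windows also govern population membership.

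Protocol 8.1 lets the investigator "discontinue the participant from study treatment at any time and initiate appropriate alternative therapy". For culture-confirmed persistence, protocol Section 9 places alternative therapy "either on or after the TOC Visit, based on availability of results". Protocol Table 2 adds: "Any participant that withdraws before TOC should have all bacteriology and NAAT assay collections performed as indicated at the TOC Visit".

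**The concern.** Criteria 2 and 3 work against each other. Criterion 3 goes out of its way to keep participants who needed another antibiotic for the same gonorrhea. Their response is already fixed as failure and a culture cannot change it. Yet criterion 2 makes their membership depend on a culture. Of two fully dosed participants treated again before TOC, one with a windowed culture counts as a failure and one without disappears from numerator and denominator alike.

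SAP 7.1.6.3 makes the ME analysis the supplementary analysis of the primary endpoint, by the primary method, in a noninferiority trial. Readers will look to it for agreement with Micro-ITT. A membership rule that removes only failures raises the rate of whichever arm it touches. Sites know the assigned treatment, so unequal losses between arms are possible.

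**Working it through.** **Step 1: the rules side by side.** Take a fully dosed participant with ceftriaxone-susceptible baseline NG, no major deviation, and another systemic antibiotic for gonorrhea before TOC.

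| | Culture result in Day 4–10 | No usable culture in Day 4–10 |
|---|---|---|
| Table 2 response | Failure | Failure |
| Micro-ITT | In, failure | In, failure |
| ME criterion 3 | Met (exception) | Met (exception) |
| ME criterion 2 | Met | Not met |
| ME analysis | In, failure | Out |

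A culture taken only at a Day 2 or 3 visit falls in the right-hand column even if NG-positive, because it gets no TOC label.

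**Step 2: the plan's own figure.** Protocol 10.2.1 has 200 per arm, 90% success in both, margin −10%, one-sided 0.025, and power of about 91%. The standard error is √(2 × 0.9 × 0.1 / 200) = 0.030. Power = Φ(0.10/0.030 − 1.96) = Φ(1.373) = 91.5%. The figure reproduces. It concerns Micro-ITT and is untouched by this point.

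**Step 3: effect on one arm's ME rate.** Let S be successes, n the participants if these failures are kept, and k the number dropped. The shift is S/(n − k) − S/n = S·k/[n(n − k)], which is positive whenever k > 0 and S > 0. The documents do not give k; values of 1 to 5 are assumed.

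| S/n | Kept | k = 1 | k = 3 | k = 5 |
|---|---|---|---|---|
| 180/200 | 90.0% | 90.5% | 91.4% | 92.3% |
| 180/190 | 94.7% | 95.2% | 96.3% | 97.3% |

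That is about 0.5 point per excluded participant per 200.

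**Step 4: effect on the difference** (gepotidacin minus comparator; unstratified Miettinen-Nurminen 95% CI; 180 successes per arm; n = 200 before exclusions).

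| Dropped | Difference | 95% CI |
|---|---|---|
| none | 0.0 | −6.05 to 6.05 |
| 5 gepotidacin | +2.3 | −3.4 to 8.1 |
| 5 comparator | −2.3 | −8.1 to 3.4 |
| 5 in each arm | 0.0 | −5.5 to 5.5 |

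The sign follows the arm that loses more. Equal losses from arms of equal size only rescale an existing difference by n/(n − k), here 200/195 = 1.026.

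**Step 5: can the noninferiority reading change?** Only in assumed borderline data.

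- Assume 166/180 v 178/180 with all kept: −6.7 (−11.7 to −2.7), noninferiority not met. Dropping 1 or 2 gepotidacin failures leaves lower limits of −11.1% and −10.5%, still not met. Dropping 4 (166/176) gives −9.2%, met. Dropping 4 gepotidacin and both comparator failures (166/176 v 178/178) gives −10.15%, not met.
- Assume 171/190 v 180/190 with all kept: lower limit −10.45%, not met. Dropping 1 gepotidacin failure (171/189) gives −9.9%, met; dropping 3 (171/187) gives −8.8%.
- At 90% in both arms with 180 each (162/180), dropping 4 gepotidacin failures moves the lower limit from −6.4% to −4.1%; it is met either way.

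**The case against.** The strongest reply is that requiring an observed culture is what microbiologically evaluable means. Table 2 also scores participants with no sample or no visit as failures. If failure by rule were enough to stay in ME, criterion 2 would have no purpose. This holds for participants who simply did not return. It does not hold here, because ME already keeps early-treated participants whose outcome is Unable to determine. For them the culture decides only whether the failure is counted.

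Other parts of the reply stand:

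- A reader might take protocol 8.1 as the direct route into the gap. It concerns stopping study treatment. Comparator dosing ends on site on Day 1, and a gepotidacin participant stopped before the second dose already fails criterion 1. The gap concerns fully dosed participants only.
- The planned path limits the numbers: therapy for persistence comes at or after TOC, early withdrawals are asked for TOC samples, and the analysis window runs to Day 10.
- A reader might infer that culture-proven failures are being removed. The documents do not say so. The failure comes from the rule on recorded antibiotic use, and no positive culture is required.
- The exclusions will be partly visible. SAP 6.1.1, Table 1.108 and Listing 103 show population exclusions; Tables 2.341 and 2.342 cover undetermined outcomes and non-study systemic antibiotics.

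**Conclusion.** The inconsistency is real and confined to the supplementary ME, ME Rectal and ME Pharyngeal analyses. As written, criterion 2 removes rule-defined failures that criterion 3 is worded to keep, and each removal raises that arm's ME success rate by about 0.5 point per 200. The primary Micro-ITT result and its power do not change.

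Two stronger readings are not supported. The first is that the ME analysis is biased toward noninferiority. That requires gepotidacin to lose proportionally more of these failures than the comparator, and nothing in the documents shows this; a heavier comparator loss moves the difference the other way. The second is that the ME conclusion would flip. The flips in Step 5 rest on assumed borderline counts and one-sided losses, and no decision rule depends on ME. The number affected is not given and may be zero. This is a cheap improvement worth making, not a threat to the trial's conclusion.

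**What to change.** In criterion 2 of the three culture-based ME populations (SAP Section 4; protocol 10.3 for ME), after the culture requirement add: *or received another systemic antibiotic for the current infection before TOC (scored microbiological failure per Table 2)*. In the protocol the matching table is Table 5. Leave criteria 1, 3 and 4 unchanged. Report the number of participants who enter through this clause by arm and body site. Make the change before unblinding, since SAP Section 4 applies part of the ME rules programmatically to unblinded data.

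The cost is one clause in each document, a line of programming and a small count table. The data are already collected: protocol 7.7 requires antibiotic use to be recorded with reason and dates. The downside is that ME success rates may be slightly less favourable. If no participant qualifies, the results do not change.
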